6.2.2.2. Cycle 1 Day 4 and Day 7 (GO Treatment)

- Laboratory tests, PE, and vital signs will be conducted as described in [Schedule of Activities \(Table 1\)](#). Vital signs will also be performed 2 hours after the infusion is complete.
- For the dose calculation and adjustment of GO, if the patient experiences a weight loss or gain >10% from the prior record of weight, the body surface area (BSA) and the amount of GO required for dose preparation must be re-calculated (maximum dosage up to one vial).
- Full recovery from hematologic toxicities is not a requirement for administration of the second or third dose on Days 4 and 7, respectively.
- Pre-medication should be given before dosing. See [Section 5.4.1](#) and [Section 5.4.2](#) for administration of premedication and GO, respectively.

- Pharmacokinetic (all patients) 

 and triplicate ECGs
will be collected according to [Schedule of Activities \(Table 2\)](#). If the dosing day is delayed beyond Day 4, these samples are to be collected on the day of dosing.

- Adverse events should be documented and recorded using NCI CTCAE version 4.03 (see [Section 8](#)).
- Concomitant medications and treatments will be recorded.

6.2.2.3. Cycle 1 Day 10 (Post-GO Period)

- Laboratory tests, PE, body weight, and vital signs will be conducted according to [Schedule of Activities \(Table 1\)](#).

- Pharmacokinetic (all patients), pharmacodynamic (only for patients 18 years or older), and metabolic profiling (only for patients 18 years or older) samples will be collected according to [Schedule of Activities \(Table 2\)](#).
- Patients with suspected extramedullary disease will have imaging assessment (eg, CAT or MRI) of all known disease sites.
- Adverse events should be documented and recorded using NCI CTCAE version 4.03 (see [Section 8](#)).
- Concomitant medications and treatments will be recorded.

6.2.2.4. Cycle 1 Days 15 and 21 (Post-GO Period)

- Laboratory tests (except CBC and differential counts) will be conducted according to [Schedule of Activities \(Table 1\)](#).
- Starting with Day 15, CBC and differential counts will be examined 3 times a week until having determination of remission status (see [Section 7.5](#)); subsequently CBC and differential counts will be collected once weekly until EOT visit (ie, 36 days after the last dose of GO) or until start of subsequent anticancer therapy, eg, Cycle 2, consolidation and/or conditioning regimen (see [Schedule of Activities Table 1](#)).
- Pharmacokinetic (all patients) ^{CC1} according to [Schedule of Activities \(Table 2\)](#).
- Blood sample will be collected for the measurement of antibodies to GO (ADA) and neutralizing antibody (NAb) on Days 15 and 21.
- Patients with extramedullary disease during screening or clinically suspicious after GO near the scheduled day for bone marrow aspiration (and biopsy if applicable) will have imaging assessment (eg, CAT or MRI). (Day 21)
- Efficacy evaluation and determination of remission status will be assessed by peripheral blood and bone marrow aspiration (and biopsy if applicable) after recovery of blood counts is observed, typically between Day 21 and Day 28. This evaluation should be conducted prior to Cycle 2 (if administered) or EOT (ie, 36 days after last the dose of GO).
- Adverse events should be documented and recorded using NCI CTCAE version 4.03 (see [Section 8](#)).
- Concomitant medications and treatments will be recorded.

6.2.3. Cycle 2

The second cycle will be allowed at the investigator's discretion for patients who meet selected dosing criteria after Cycle 1 (see [Section 7.5](#)). Cycle 2 Day 1 must be started no later than 42 days after the last dose of GO (ie, Cycle 1 Day 7).

6.2.3.1. Cycle 2 Day 1

- On Day 1 patients may be admitted at the site for 24 hours as per investigator's discretion. Hospitalization beyond Day 1 will be per standard practice and investigator judgment. If there is prolongation of hospitalization, consider if SAE criteria are met (see [Section 8.2.4](#)).
- Laboratory specimen will be collected per the [Schedule of Activities \(Table 1\)](#) and assessed per [Section 7](#). Results of complete blood counts, and serum chemistry tests must be checked before dosing. Patients will be weighed for BSA calculation. Physical examination (PE) performed with clinical judgment evaluating potential areas of AML relapse and any clinically significant abnormalities which may include the following body systems: general appearance, skin, head/eyes/ears/nose/throat, heart, lungs, testes, abdomen, extremities, neurological, back/spinal, and lymph nodes; including worsening of medical history conditions.
- Vital signs including blood pressure, pulse and temperature will be performed prior to GO infusion and 2 hours after the infusion is complete (see [Table 1](#)).
- Pre-medication should be given before GO infusion. [Section 5.4.1](#) and [Section 5.4.2](#) for administration of premedication and GO, respectively.
- Electrocardiograms (ECGs) will be collected in all patients according to [Schedule of Activities \(Table 2\)](#) and as described in [Section 7.1](#). The ECGs will be collected in triplicate (3 consecutive ECGs approximately 2 minutes apart). Predose ECGs will be performed prior to GO dosing, after administration of premedications. Triplicate ECGs will also be performed prior to selected serial PK draws, around the time when the C_{max} is expected and immediately before the end of the infusion, ie, prior to the Hour 2 PK sample collection (within 15 minutes).³
- PK collections (all patients) will include predose (Hour 0) and Hour 2 as described in [Schedule of Activities \(Table 2\)](#).
- Adverse events should be documented and recorded using NCI CTCAE version 4.03 (see [Section 8](#)).
- Concomitant medications and treatments will be recorded.

6.2.3.2. Cycle 2 Day 4 and Day 7 (GO Treatment)

- Laboratory tests, PE, and vital signs will be conducted as described in [Schedule of Activities \(Table 1\)](#). Vital signs will also be performed 2 hours after the infusion is complete.
- For the dose calculation and adjustment of GO, if the patient experiences a weight loss or gain >10% from the prior record of weight, the body surface area (BSA) and the amount of GO required for dose preparation must be re-calculated (Maximum dosage will be up to one vial).
- Full recovery from hematologic toxicities is not a requirement for administration of the second or third dose on Day 4 or 7, respectively.
- Pre-medication should be given before dosing. See [Section 5.4.1](#) and [Section 5.4.2](#) for administration of premedication and GO, respectively.
- Pharmacokinetic (all patients) and triplicate ECGs will be collected on Day 7 according to [Schedule of Activities \(Table 2\)](#). If the dosing day is delayed beyond Day 4, these samples are to be collected on the day of dosing.
- Adverse events should be documented and recorded using NCI CTCAE version 4.03 (see [Section 8](#)).
- Concomitant medications and treatments will be recorded.

6.2.3.3. Cycle 2 Day 10 (Post-GO Period)

- Laboratory tests will be conducted according to [Schedule of Activities \(Table 1\)](#).
- Patients with suspected extramedullary disease will have imaging assessment (eg, CAT or MRI) of all known disease sites.
- Adverse events should be documented and recorded using NCI CTCAE version 4.03 (see [Section 8](#)).
- Concomitant medications and treatments will be recorded.

6.2.3.4. Cycle 2 Days 15 and 21 (Post-GO Period)

- Laboratory tests (except CBC and differential counts) will be conducted according to [Schedule of Activities \(Table 1\)](#).
- Starting with Day 15, blood cell and differential counts will be examined 3 times a week until having determination of remission status (see [Section 7.5](#)); subsequently CBC and differential counts will be collected once weekly until EOT visit (ie, 36 days after the last dose of GO) or until start of subsequent anticancer therapy, eg, consolidation and/or conditioning regimen (see [Schedule of Activities Table 1](#)).

- Blood sample will be collected for PK assessment and the measurement of antibodies to GO (ADA) and neutralizing antibody (NAb) on Days 15 and 21.
- Patients with extramedullary disease during screening or clinically suspicious after GO near the scheduled day for bone marrow aspiration (and biopsy if applicable) will have imaging assessment (eg, CAT or MRI).
- Determination of remission status will be assessed by peripheral blood and the bone marrow aspiration (and biopsy if applicable) after recovery of blood counts is observed, , typically between Day 21 and Day 28. This evaluation should be conducted prior to EOT (ie, 36 days after the last dose of GO).
- Adverse events should be documented and recorded using NCI CTCAE version 4.03 (see [Section 8](#)).
- Concomitant medications and treatments will be recorded.

6.2.4. The End-of-Treatment (EOT) Visit (36 Days after the Last Dose of GO)

- This visit is required for all patients. It occurs 36 days after the last dose of GO. However, in the event that a patient requires initiation of a consolidation treatment or another anti-cancer therapy, the end-of-treatment visit, including procedures (laboratory tests, PE, sampling for PK and ADA/NAb assays), should be performed before the initiation of a consolidation treatment or subsequent anti-cancer therapy. Adverse events, safety laboratory tests, and associated concomitant medications must continue to be collected in the CRF through at least 36 days after the last dose of GO or start of subsequent therapy, eg, consolidation and/or conditioning regimen, whichever occurs first.
- Adverse Event (AE) Assessments should be documented and recorded at each visit using NCI CTCAE version 4.03 up to EOT visit, or start of subsequent anticancer therapy, eg, consolidation and/or conditioning regimen, whichever occurs first.
- Concomitant medications and treatments will be recorded up to 36 days after the last dose of study treatment or starting subsequent anticancer therapy (eg, consolidation or conditioning regimen).
- EOT visit procedures and tests include the following:
 - Blood sample collection for PK assessment and ADA/NAb measurement;
 - Limited physical examination, with clinical judgment to evaluate potential areas of AML relapse and any clinically significant abnormalities which may include the following body systems: general appearance, skin, head/eyes/ears/nose/throat, heart, lungs, testes, abdomen, extremities, neurological, back/spinal, and lymph nodes; including worsening of medical history conditions;

- Laboratory evaluations, including pregnancy test, according to the [Schedule of Activities \(Table 1\)](#).
- Disease assessment for final determination of remission status should be conducted no later than 36 days after last dose of GO (EOT) or/and prior to the start of subsequent anticancer therapy (eg, consolidation and/or conditioning regimen).

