The Schedule of Activities table provides an overview of the protocol visits and procedures. Refer to the **STUDY PROCEDURES** (see **Section 6**) and **ASSESSMENTS** (see **Section 7**) sections of the protocol for detailed information on each procedure and assessment required for compliance with the protocol. The investigator may schedule visits (unplanned visits) in addition to those listed on the Schedule of Activities table, in order to conduct evaluations or assessments required to protect the well-being of the patient.

Table 1. Schedule of Activities

Schedule Day ¹	Screening	Cycle 1						Cycle 2 (if administered)						EOT	Follow-up Period ¹⁹		
		GO Treatment			Post-GO Period			GO Treatment			Post-GO Period						
		C1 D1	C1 D4	C1 D7	C1 D10	C1 D15	C1 D21	C2 D1	C2 D4	C2 D7	C2 D10	C2 D15	C2 D21				
Schedule Day ¹	<28 days prior to enrollment														Every 12 weeks		
Visit window (Days)					±1	±1	±1				±1	±1	±1	±2	±7		
Informed consent & assent ³	X																
Immunophenotyping (including CD33) ⁴	X																
CCI		■															
ECG (in triplicate) ⁶	X	X	X	X				X		X							
Pharmacokinetic samples ⁷		X	X	X	X ⁷	X ⁷	X ⁷	X ⁷		X ⁷		X ⁷	X ⁷	X			
Medical history ⁸	X																
Body weight	X	X	X	X				X	X	X							
Vital signs/PE	X	X	X	X				X	X	X							
ECOG PS score ⁹	X	X						X									
Imaging assessment ¹⁰	X ¹⁰				X ¹⁰						X ¹⁰						

Table 1. Schedule of Activities

	Screening	Cycle 1						Cycle 2 (if administered)						EOT	Follow-up Period ¹⁹		
		GO Treatment			Post-GO Period			GO Treatment			Post-GO Period						
		C1 D1	C1 D4	C1 D7	C1 D10	C1 D15	C1 D21	C2 D1	C2 D4	C2 D7	C2 D10	C2 D15	C2 D21				
Schedule Day ¹	<28 days prior to enrollment														Every 12 weeks		
Visit window (Days)					±1	±1	±1				±1	±1	±1	±2	±7		
Safety Laboratory¹¹																	
CBC and differential counts ¹²	X	X	X	X	X	X ¹²		X	X	X	X	X ¹²		X			
Chemistry	X	X	X	X	X	X	X	X	X	X	X	X	X	X	X ¹⁷		
Urinalysis	X				X	X											
Coagulation (PT, aPTT, fibrinogen)	X	X	X	X	X	X		X	X	X	X	X					
Pregnancy test	X ¹³													X ²⁰			
HIV, Hepatitis B, and Hepatitis C evaluation ¹⁴	X																
Pre-medication		X	X	X				X	X	X							
BM examination and disease assessments ¹⁵						X ¹⁵						X ¹⁵					
Serious and non-serious adverse event monitoring ¹⁶	X	X	X	X	X	X	X	X	X	X	X	X	X	X	X ¹⁷		
Concomitant medications and treatment ¹⁸	X	X	X	X	X	X	X	X	X	X	X	X	X	X	X		
Survival follow-up ¹⁹															X ²¹		

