6. ECGs will be in triplicate (3 consecutive ECGs approximately 2 minutes apart). All ECGs will be sent to an ECG core laboratory vendor. ECG at screening will be used to determine patient eligibility. Ideally, the patient will be supine or reclined in a semi recumbent position for the entire infusion and for both pre- and post- infusion ECGs. To minimize artifact, the patient should not change position between the pre- and post-infusion ECGs. Additional ECGs may be done if clinically required. See [Table 2](#) for additional collection time points.
7. Pharmacokinetic samples: See [Table 2](#) for additional time points.
8. Medical History: To be collected within 28 days prior to first dose. Includes date of initial diagnosis with FAB subtype, prior AML therapies including HSCT and outcomes, and cytogenetics. Also, review study eligibility.
9. ECOG PS: Assessment is not required on Day 1 if acceptable screening assessment is done within 7 days prior to the start of investigational drug.
10. Patients with suspected extramedullary disease will have imaging assessment (eg, CAT or MRI) of all known disease sites.
11. Days 1, 4, and 7 laboratory samples should be collected prior to dosing.
12. Three times a week after GO dosing until determination of remission status (see [Section 7.5](#)); subsequently CBC and differential counts will be collected once weekly until EOT (or until start of Cycle 2 (if administered) or start of subsequent anticancer therapy).
13. Pregnancy test: Required in less than 7 days prior to Day 1.
14. Evaluations of HIV and hepatitis B serological tests and hepatitis C tests (see [Section 6.1](#)).
15. Efficacy evaluation and determination of remission status by blood and bone marrow aspiration (and biopsy if applicable) after recovery of blood counts is observed and/or at a maximum of 36 days after the last dose of GO treatment.
16. Adverse Event (AE) Assessments: Adverse events should be documented and recorded at each visit using NCI CTCAE version 4.03 up to 36 days after the last dose of GO or start of subsequent anticancer therapy, (eg, consolidation or conditioning regimen), whichever occurs first. Patients must be followed for AEs according to [Section 8](#). Sites should report related SAEs including VOD/SOS as warranted. Any occurrence of VOD/SOS is to be reported as SAE to Pfizer Safety and recorded in the case report form (CRF see [Section 7.4.1](#)).

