8.1.4.1. Reporting SAEs to Pfizer Safety

All SAEs occurring in a patient during the active collection period are reported to Pfizer Safety on the CT SAE Report Form.

SAEs occurring in a patient after the active collection period has ended are reported to Pfizer Safety if the investigator becomes aware of them; at a minimum, all SAEs that the investigator believes have at least a reasonable possibility of being related to investigational product must be reported to Pfizer Safety. Follow up by the investigator continues throughout and after the active collection period and until the event or its sequelae resolve or stabilize at a level acceptable to the investigator, and Pfizer concurs with that assessment.

If a patient starts a subsequent anticancer therapy (eg, consolidation, and/or conditioning regimen, or HSCT), SAEs occurring during the above-indicated active collection period (ie, within 36 days of last dose of GO) must still be reported to Pfizer Safety irrespective of any intervening treatment and causality.

Incidence of VOD/SOS will be reported for the entire study duration of 12 months, regardless of causality, or start of subsequent anticancer therapy (eg, consolidation and/or conditioning regimen, or HSCT). All cases of VOD/SOS must be reported as SAEs (recorded on the CRF and CT SAE Report Form).

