8.1.4.2. Recording Non-serious AEs and SAEs on the CRF

During the active collection period, both non-serious AEs and SAEs are recorded on the CRF.

Follow-up by the investigator may be required until the event or its sequelae resolve or stabilize at a level acceptable to the investigator, and Pfizer concurs with that assessment.

If a patient begins a new anticancer therapy, the recording period for non-serious AEs ends at the time the new treatment is started; however, SAEs must continue to be recorded on the CRF during the above-indicated active collection period.

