The active safety monitoring duration will be up to 36 days after the last dose of GO or starting of subsequent anticancer therapy, including consolidation and/or conditioning regimens, whichever occurs first. Any events of veno-occlusive disease (VOD) and sinusoidal obstruction syndrome (SOS) will be reported as serious adverse event (SAE) during the study duration. Details of the HSCT will be collected in order to assess the impact of the fractionated regimen of GO on the risk of VOD/SOS with previous or subsequent HSCT.

After receiving the study treatment, blood cell and differential counts will be examined 3 times a week after GO dosing until having determination of remission status; subsequently CBC and differential counts will be collected once weekly until 36 days after the last dose of GO or until start of subsequent anticancer therapy, e.g., consolidation or conditioning regimen.

Efficacy evaluation and determination of remission status by blood and bone marrow aspiration (and biopsy if applicable) will be conducted at the end of each cycle after recovery of blood counts is observed or at a maximum of 36 days after the last dose of GO treatment (EOT) using European Leukemia Net (ELN 2017) recommendations.

Study duration for each patient is a total of 12 months from enrollment, survival data will be collected for the study duration of 12 months.

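### The visit section and schedule stop AE recording at new anticancer therapy with no general SAE exception, while Section 8.1.4 requires SAEs to 36 days, so some SAEs may be missing from the CRF

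*Protocol*

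**What the plan says.** Two rules for the end of AE collection stand side by side.

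**Stop at the earlier date.** The first bullet of Protocol Section 6.2.4 has CRF collection of AEs run "through at least 36 days after the last dose of GO or start of subsequent therapy, eg, consolidation and/or conditioning regimen, whichever occurs first". The second bullet gives an end point: AEs are recorded "up to EOT visit, or start of subsequent anticancer therapy, eg, consolidation and/or conditioning regimen, whichever occurs first". Table 1 footnote 16 says the same, "up to 36 days after the last dose of GO or start of subsequent anticancer therapy, (eg, consolidation or conditioning regimen), whichever occurs first", and it is attached to the row "Serious and non-serious adverse event monitoring". The footnote goes on to ask sites to report SAEs that are related, including VOD/SOS, and refers to Section 8. Protocol Sections 3 and 7.4 describe a safety window with the same two end points. So does SAP Section 2.2: "The active safety monitoring duration will be up to 36 days after the last dose of GO or starting of subsequent anticancer therapy". SAP Section 3.5 repeats it.

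**SAEs continue.** Protocol Section 8.1.4 sets an active collection period for AEs and SAEs of at least 36 calendar days after the final dose, with no cut at new therapy. Section 8.1.4.2 ends only non-serious events when a new treatment starts; beyond that, "SAEs must continue to be recorded on the CRF during the above-indicated active collection period". Section 8.1.4.1 adds that SAEs in this period "must still be reported to Pfizer Safety irrespective of any intervening treatment and causality".

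VOD/SOS is handled separately and goes on the CRF for 12 months under either rule (Sections 6.2.5, 7.4.1 and 8.4.3).

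**The concern.** For an SAE other than VOD/SOS that starts after new anticancer therapy but within 36 days of the last GO dose, one group of passages ends recording and the other requires it. No passage states which prevails. Footnote 16 adds a second conflict, because it asks for related SAEs while Section 8.1.4.1 sets causality aside.

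AEs are a secondary endpoint, and the study answers post-marketing safety requirements. If sites follow different rules, the completeness of the SAE tables for this interval depends on which page each site worked from, and the tables would not show it.

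**Working it through.** No statistical figure in the plan is at issue. The check is a comparison of texts plus one count of days.

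**1. Which sentences really stop recording.** The first bullet of Section 6.2.4 contains the words for a minimum, so it cannot carry the point alone. The second bullet and footnote 16 are true end points. Neither names SAEs in stating its end point. The second bullet uses the undifferentiated term for adverse events; footnote 16 reaches serious events through the label of its row.

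**2. Apply both rules to an event that starts between new therapy and 36 days after the last dose.**

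| Event | 6.2.4 second bullet and footnote 16: CRF | 8.1.4.2: CRF | Sponsor safety (8.1.4.1, 8.4.1) |
|---|---|---|---|
| Non-serious AE | No | No | No |
| VOD/SOS | Yes (12-month rule) | Yes | Yes |
| Most other SAEs | No | Yes | Yes |
| Febrile neutropenia or neutropenic sepsis, unrelated, not Grade 5 | No | Yes | No |

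The third row is the general conflict, with sponsor safety as a backstop. The fourth has no backstop. Section 8.4.1 tells investigators not to report these two events as SAEs unless they are judged related or are Grade 5, and relies on the CRF to hold them. Under the first rule they could appear in neither record.

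**3. Does the schedule prompt the site?** Section 6.2.4 moves the EOT visit to before new therapy. Visits are then every 12 weeks (Section 6.2.5). The follow-up cell of the AE row carries footnote 17, which concerns VOD/SOS only, and the list of follow-up data in Section 6.2.5 names no other SAEs. The cycle-visit AE instructions point to Section 8, but the AE bullets of Section 6.2.4 do not. Omission is therefore plausible.

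**4. Does the analysis depend on it?** SAP Section 3.5.1 counts every collected AE after first dose as treatment emergent. SAP Section 6.6.1 takes seriousness from the AE CRF. SAP Sections 5.2.4 and 5.2.5 close the last cycle at the earlier of last dose plus 36 days and new therapy, and assign later AEs to a Follow-up category that Section 6.6.1 tabulates. The disputed events fall in that category, and its content depends on what sites entered.

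**5. Length of the disputed interval.** Inputs: last dose of the cycle on Day 7; 36-day period; remission assessment usually between Day 21 and Day 28 (Sections 6.2.2.4 and 6.2.3.4). Assumption: new therapy starts on the day of that assessment.
- End of period: 7 + 36 = Day 43.
- Therapy on Day 28: 43 − 28 = 15 days, or 15/36 = 42% of the post-dose period.
- Therapy on Day 21: 43 − 21 = 22 days, or 22/36 = 61%.
- Therapy on Day 43 or later: 0 days.

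These are calendar days per affected patient, not a proportion of SAEs.

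**The case against.** The case for leaving this alone is substantial.

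- Section 8 is the only place that separates serious from non-serious events, and it is explicit. The table in Section 8.1 has all SAEs recorded on the CRF. Footnote 16 and SAP Section 3.5 both refer to the protocol's Section 8. A careful site would follow it. This stands as a reason to say that events may be omitted. It does not remove the contradiction, since footnote 16 refers to Section 8 and in the same note gives a different end point and a narrower SAE request.
- Most of these SAEs still go to sponsor safety, and Section 8.1.1 requires the CRF and the SAE form to agree, which gives a cross-check. This stands, except for the two events in Section 8.4.1.
- Transplant conditioning is unlikely to fall in the interval. The protocol recommends at least 2 months between the last GO dose and HSCT. With the SAP's month of 30.4375 days that is 60.9 days, so conditioning would have to start about 60.9 − 36 = 25 days before transplant. This stands; other therapy is the likelier route into the interval.

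Three stronger readings are tempting, and the documents do not support them:

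- A reader might infer that SAEs will certainly be captured at some sites and lost at others. The documents show a risk, and the loss would mostly be from the CRF alone.
- A reader might infer from SAP Sections 2.2 and 3.5 that the analysis drops SAEs after new therapy. Those sections describe the monitoring period. SAP Section 3.5 runs the on-treatment period to the end of study follow-up, and no table rule excludes a collected SAE.
- A reader might take the 19 responders among 57 patients in the cited Phase 2 study to mean that two thirds (38/57) move early to other therapy. Non-response is not the rate of starting therapy before Day 43: non-responders may die, have no further treatment or qualify for Cycle 2, and that study gave consolidation after GO. Section 5.7 also bars other anticancer therapy until remission status is determined, which Section 7.5 allows to take up to 36 days after the last dose.

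**Conclusion.** The point holds as an internal inconsistency in the protocol. The second bullet of Section 6.2.4 and Table 1 footnote 16 conflict with Sections 8.1.4 to 8.1.4.2 on whether non-VOD SAEs are recorded after new therapy, and footnote 16 conflicts with Section 8.1.4.1 on causality. The consequence is possible under-recording on the CRF, with unrelated, non-Grade 5 febrile neutropenia and neutropenic sepsis the most exposed.

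The interval is 15 to 22 days per affected patient if new therapy starts at the usual assessment and the last dose is on Day 7; it shrinks to zero by Day 43. The number of patients and of SAEs affected cannot be derived from the documents. VOD/SOS capture and the primary QTc analysis are untouched. The inconsistency should be corrected, but it does not by itself undermine the safety results.

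**What to change.** - **Protocol text.** Reconcile Section 6.2.4, Table 1 footnote 16 (including its restriction to related SAEs) and the safety-window wording in Sections 3 and 7.4 with Section 8.1.4. State three windows separately: non-serious AEs to the start of new therapy or the end of the active collection period; SAEs to 36 days after the last GO dose whatever treatment intervenes; VOD/SOS to 12 months.
- **SAP text.** Align the description in Sections 2.2 and 3.5 for consistency only. No table rule changes.
- **Data.** Before database release, compare SAEs on the CRF with the safety database for each patient who began new therapy within 36 days of the last dose. Query those sites directly for febrile neutropenia and neutropenic sepsis, which the comparison cannot find. This step also covers patients who passed through the interval before the text is corrected.

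The cost is a text alignment, one reconciliation listing and a limited set of site queries. Section 8 already requires the data.
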